8.3.3.3. AE Resolution

All AEs/SAEs must be followed until resolution. Refer to Appendix 2, Section 10.2.5.4 for details.

8.3.4. Regulatory Reporting Requirements for SAEs

Refer to Appendix 2, Section 10.2.6 for details regarding SAE reporting.

For the purposes of regulatory reporting, this study will be conducted like a post-marketing study, as the product used is a marketed product approved in the country.

Prompt notification by the investigator to the sponsor of a SAE is essential so that legal obligations and ethical responsibilities towards the safety of participants and the safety of a study intervention under clinical investigation are met.

The sponsor or delegate has a legal responsibility to notify both the local regulatory authority and potentially other regulatory agencies about the safety of the study intervention under clinical investigation. The sponsor will comply with country-specific regulatory requirements relating to safety reporting to the regulatory authority, IRBs/IECs, and investigators.

All fatal and life-threatening SUSARs are to be reported to South African Health Products Regulatory Authority (SAHPRA) within 7 calendar days after first knowledge with a complete report to be submitted within an additional 8 calendar days. SUSARs that are not fatal or life threatening need to be reported to SAHPRA no later than 15 calendar days after first knowledge. An investigator who receives a SUSAR report or other specific safety information (e.g., summary or listing of SAEs) from the sponsor will review and file it. A tracker of all such reports received from the CRO will be maintained by the site. The PI will notify the IRB/IEC, if appropriate and according to local requirements. IRB/IEC submissions will be conducted per the local IRB/IEC SOP.

The sponsor will prepare, distribute and submit SUSAR reports according to local regulatory requirements. The CRO, on behalf of the sponsor will submit the SUSAR reports to SAHPRA.

Refer to Appendix 2, Section 10.2.6 for details regarding SAE reporting.

8.3.5. Death Events

Any untoward medical occurrence resulting in death is reported as an SAE. The cause of death will be appropriately documented in the SAE report form and supporting evidence will be provided.

8.3.6. Latent TB infection and TB disease

Participants in this trial will be managed according to current national and/or international guidelines, in accordance with ethical standards. A recent international guideline (*Latent tuberculosis infection. Updated and consolidated guidelines for programmatic management.* [WHO, 2018b]) recommends that in countries with a high TB incidence, children aged ≥ 5 years, adolescents and adults who are household contacts of people with bacteriologically confirmed pulmonary TB who are found not to have active TB may be given preventive therapy (*Conditional recommendation, low-quality evidence. New recommendation*). Household contact is used in this context as a proxy for possible *Mtb* infection, and associated risk for progression to TB disease, in countries where testing for infection is not routine.

This trial will test adolescent participants for sustained *Mtb* infection using the QFT assay. Since it would be illogical to offer preventive therapy based on household contact status when serial QFT results are available, all participants with sustained QFT conversion will either be referred for TB preventive therapy (TPT) regardless of whether or not they are household contacts of a confirmed TB case, or be offered TPT by the site. Participants with transient QFT conversion, i.e., participants who's initial QFT positive result reverts to negative within 6 months, will not be referred for preventive therapy.

All participants who are QFT positive (from screening throughout study period) will be educated on the symptoms of TB and the benefits of early diagnosis and treatment.

Active surveillance for signs and symptoms compatible with incident TB disease, e.g., cough, fever, fatigue or night sweats, for longer than two weeks, or loss of weight / insufficient weight gain or growth, will continue throughout the study.

Participants with suspected TB disease will be tested for HIV infection and will be asked to provide two sputum samples or other appropriate samples for smear microscopy, mycobacterial culture, and GeneXpert.

Participants with a microbiological, radiological, and/or clinical diagnosis of TB disease will be referred to the NTP for TB treatment which is provided free of charge by the NTP.

A bacteriologically confirmed case of active TB disease will be defined as clinical evidence of TB with positive *Mtb* mycobacteria growth indicator tube culture, or GeneXpert *MTB*/rifampicin (Cepheid, USA), from sputum or an extra-pulmonary site.

A clinical case of active TB disease will be defined as clinical and/or radiographic evidence of active TB disease that is not bacteriologically confirmed.

8.4. Treatment of Overdose

If a dosing error occurs, the investigator, safety physician and medical monitor need to be informed as soon as possible.

8.5. Pharmacokinetics

PK parameters are not evaluated in this vaccine study.

8.6. Pharmacodynamics

Pharmacodynamic parameters (other than characterization of the immune response to vaccination) are not evaluated in this vaccine study.

8.7. Genetics

Germline genetic information may be assessed to aid in the interpretation of study results related to the host response to BCG vaccination and to *Mtb* infection. Germline genetic analyses may include HLA typing, $Fc\gamma$ receptor and NK cell genotyping, and assessment of other genetic information that may influence vaccine-induced and infection-induced responses, as well as susceptibility to infectious diseases. Germline genetic information will not be used for analyses related to paternity, ancestry or hereditary diseases. See Appendix 4, Section 10.4 regarding information for use and analysis of DNA samples.

8.8. Biomarkers

Collection and analyses of blood samples for biomarker research and identification of potential correlates of risk for and correlates of protection from sustained *Mtb* infection is an essential part of this study. Analytic approaches for the exploratory endpoints below will be informed by best practice and the most recent advances in biomarker discovery and systems biology.

Exploratory analyses of host characteristics, as well as host responses following vaccination, that correlate with the risk of transient and/or sustained QFT conversion will be conducted. Specific objectives and hypotheses related to these analyses will be documented and reported in a separate scientific and statistical analysis plan, prior to full unblinding of data associated with these exploratory analyses.

Exploratory endpoints may include proteomics, antibody analyses and cellular analyses (eg, NK cells, B cells, T cells), as well as candidate CoP and CoR identified in other studies.

PBMC, plasma, serum and whole blood samples will be collected at time points likely to show peak responses for cellular, humoral, and transcriptomic responses, respectively. Refer to SoA, Section 1.3 for specific time points and volumes for collection of samples. If an effect of vaccination is seen on infection with *Mtb*, immunologic assays may be conducted to search for correlates of risk or protection. Functional assays such as mycobacterial growth inhibition may also be conducted.

Transcriptome studies may be conducted using RNA sequencing or comparable techniques, which facilitate the simultaneous measurement of the relative abundances of thousands of RNA species resulting in a transcriptome profile for each blood sample. This will enable the evaluation of changes in transcriptome profiles that may correlate with biological response relating the prevention of initial and sustained QFT conversion.

Biomarkers studies using DNA-sequencing technologies such as Assay for Transposase-Accessible Chromatin with high throughput Sequencing (ATAC-seq) may be used to identify accessible chromatin sequences from small cell numbers, e.g., PBMCs, to generate epigenomic profiles of immune cells. Histone modification and other epigenetic modifications that are potentially affected by vaccination and/or *Mtb* infection may be analyzed. These genetic and epigenetic studies aim to identify correlates of risk and correlates of protection for *Mtb* infection, for sustained *Mtb* infection, and TB disease. If any CoRs or CoPs are identified in other studies, validity of such correlates may be tested using data from this this study.

Plasma and/or serum may be analyzed for soluble immune mediators by quantification using multiplex assays.

Samples will be stored according to local regulations at a facility selected by the sponsor.

Collected samples will be used for protocol related biomarker research. In addition, only with the explicit and optional consent of study participants, samples or partial sample volumes that remain once a protocol-defined assay has been completed, may be stored and used for purposes other than protocol-related endpoints. Such "future research studies" would include assay development, assay quality control and development of methods related to tuberculosis research and TB vaccine research, including studies that pertain to the improvement, development and quality assurance of the lab tests described in this protocol. Such future research is subject to laws and regulations of South Africa and is subject to IRB/IEC approval.

Refer to Appendix 4, Section 10.4 regarding use/analysis of DNA.

8.8.1. Immunological Assessments

Immunological outcomes may include ICS on PBMC and whole blood, phenotyping of cell subsets by flow cytometry, transcriptomics and genetic or epigenetics studies using RNA and/or DNA extracted from whole blood or white blood cells, and quantification of soluble immune mediators by multiplex assays.

The assessment of immune responses to vaccine may include the frequency of *Mtb*-, BCGand/or NTM-specific CD4 T cells positive for markers such as IFN- γ , TNF- α , IL-2 and/or IL-22. Responses will be measured by flow cytometry in the ICS assay.

Antibody titers against BCG may also be measured using ELISA, multiplex assays or functional assays (eg, mycobacterial killing assays etc).

8.8.2. Subset Assessment

For a subset of the first 80 10- to 12-year-old participants enrolled at the SATVI site, ICS will be performed directly *ex vivo* after stimulation of whole blood. Site staff will use the Study Reference Manual (provided separately) for further instructions and additional information on specimen collection and processing. All blood volumes in the table are approximate.

Note that the type of assays performed will be based on the most current information available at the time of analysis.

8.9. Health Economics

This section is not applicable.

9. Statistical Considerations

9.1. Statistical Hypotheses

Primary: Revaccination with BCG reduces the risk of sustained *Mtb* infection versus placebo in previously BCG vaccinated, QFT negative healthy adolescents.

Secondary:

- Revaccination with BCG reduces the risk of sustained *Mtb* infection versus placebo in previously BCG vaccinated, QFT negative healthy adolescents, with VE durability that lasts at least 36 months in all participants.
- Revaccination with BCG reduces the risk of sustained *Mtb* infection versus placebo in previously BCG vaccinated, QFT negative healthy adolescents, with VE durability that lasts 48 months in all participants.

650	21.9	94.0	0.2	20.8	699	783	1566
700	50.4	99.4	0.8	52.7	753	844	1688
750	77.0	> 99.9	5.3	80.2	807	904	1808
800	93.0	> 99.9	20.5	94.5	861	964	1928

Table 8: Sample Size Requirements to Ensure 75%-80% Probability of Performing the Primary Analysis within 3.5 years

Assumes equal randomization (randomization ratio 1:1)

Probability analysis occurs within 3 and 3.5 years (yrs) based on 2000 simulations, assuming 1 yr accrual, 70% of primary infection remain sustained, 5% annual drop-out rate

* Assumes 7% removed from those randomized due to QFT + result at Day 71

** Assumes additional 12% of participants will be 10 or 11 year olds, where we have limited information on attack rate and potential VE

9.3. Populations for Analyses

Analysis populations are shown in Table 9.

Population	Description
Modified intention to treat (mITT) efficacy population	All participants randomly assigned to study intervention, who received the study intervention and are QFT negative at the Day 71 visit, or if the Day 71 study visit was missed, or the QFT result was not available, the first study visit post Day 71 for which a QFT result is available. Participants will be analyzed according to the intervention to which they were randomized.
Intention to treat (ITT) efficacy population	All participants randomly assigned to study intervention and who received the study intervention. Participants will be analyzed according to the intervention to which they were randomized.
Per Protocol (PP) efficacy population	All participants in the mITT population who did not substantially deviate from the protocol procedures and who received the treatment to which they were randomized Participants who substantially deviated will be identified prior to database lock and unblinding.
Safety	All participants randomly assigned to study intervention and who received the study intervention. Participants will be analyzed according to the intervention they actually received.

9.4. Statistical Analyses

A detailed statistical analysis plan (SAP) centered on primary and secondary endpoints will be developed and finalized prior to initiation of enrollment and will further describe the participant populations to be included in each analysis, details of the statistical methods, including procedures for accounting for missing, unused, and spurious data. Some exploratory analyses may be included in this SAP. Analyses are summarized in Table 10.

Exploratory endpoint analyses, in particular those centered on immunogenicity and exploratory biomarker analyses, will be described in a separate exploratory scientific and statistical analysis plan (exploratory SSAP). Specific objectives and hypotheses related to exploratory biomarker analyses will be documented in this exploratory SSAP prior to full data unblinding and analysis.

Results from the exploratory analyses may be reported in a separate results memo and included as an addendum to the clinical study report (CSR).

Endpoint	Statistical Analysis
Primary:	
Sustained QFT conversion based on positive QFT test results (initial conversion and QFT- positive at 3- and 6-months PC)	The primary analysis will be triggered when at least 118 sustained Mtb infection events in the mITT efficacy population are accrued. A log-rank test, stratified by sex and age group (10-11 years old, 12-14 years old, and > 14 years old), will be used to evaluate differences in the distributions of event times between the BCG vaccination and placebo groups. The primary hypothesis will be met if the 1-sided p-value associated with evaluating whether the event free distribution is longer in the BCG vaccination group relative the placebo group is less than or equal to 0.025. Hazard ratios and 95% confidence intervals will be estimated using a stratified Cox proportional hazards regression model.
Secondary:	
Sustained QFT conversion based on positive QFT test results (initial conversion and QFT- positive at 3- and 6-months PC) with a follow-up of 36- and 48- months post vaccination	Two durability analyses will be performed, the first after all participants have at least 36 months of follow-up and the second after all participants have 48 months of follow- up. Log-rank tests, stratified by sex and age group (10-11 years old, 12-14 years old, and > 14 years old), will be used to evaluate differences in the distributions of event times between the BCG vaccination and placebo groups. The secondary hypotheses will be met if the 1-sided p-value associated with evaluating whether the event free distribution is longer in the BCG vaccination group relative the placebo group is less than or equal to 0.025. Hazard ratios and 95% confidence intervals will be estimated using stratified Cox proportional hazards regression models.

Table 10: Summary of Primary and Secondary Endpoints and Analyses

Endpoint	Statistical Analysis
Secondary, continued	
Safety endpoints post vaccination Solicited AEs through 7 days Unsolicited AEs through 28 days All SAEs and AESIs through Month 6 Serious ADRs through the end of the study	The incidence and 95% confidence intervals of AEs will be summarized by treatment group, overall, and by grade, intensity, and relatedness. The incidence and 95% confidence intervals of SAEs will be summarized by treatment group. Summary statistics will be generated for raw laboratory safety tests, as well as for changes from baseline, as deemed clinically appropriate.

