The duration of follow-up with semiannual QFT-testing is 4 years, as compared to two years in the Aeras 404 study. The longer follow-up will enable us to assess the duration of protection past 24 months as a secondary objective, and the statistical analysis plan will include duration of protection analyses.

The study intends to enroll adolescents from 10 years of age since the previous trial found that approximately half of the adolescents 12 to 17 years of age are already infected with *Mtb*, as assessed by QFT. Since this intervention aims to prevent sustained infection, it would therefore be meaningful to implement in an age group in which the majority are uninfected.

Another secondary endpoint is to evaluate the efficacy and durability of efficacy of BCG revaccination against primary *Mtb* infection post vaccination using an alternative definition of conversion as a change in IFN- γ concentration from <0.35 IU/mL to \geq 4 IU/mL (initial conversion only). In the Aeras 404 study, the QFT-GIT assay was used and a vaccine efficacy of ~45% was observed for this endpoint.

The rationale for this end-point is that QFT conversion above this threshold was associated with an increased risk of tuberculosis disease in infants and adults [Andrews 2017; Winje 2018, a finding that was consistent with predictions from studies in animal models [Andersen 2007]. Therefore, this alternative conversion threshold will be evaluated as a secondary exploratory objective in this trial. The QFT-GIT assay has limitations as a test for *Mtb* infection, due to intraparticipant and dynamic variability around the threshold recommended by the manufacturer (Pai, 2012; Mazurek et al, 2010). QFT-GIT assay variability appears maximal in low burden settings with low rates of *Mtb* infection. Findings from high TB burden settings with high risk of *Mtb* infection, such as South Africa, where the rate of QFT-GIT conversion is similar to the expected rate of TST conversion, are in contrast to the pattern observed in serial testing of low risk study populations, where the rate of QFT-GIT conversion has been unexpectedly high compared to TST [Pai 2012; Zwerling 2013].

In this current study the QuantiFERON®-TB-Gold-Plus assay (QFT) will be used, which is the updated version of the QFT-GIT assay.

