9.4.1.2. Secondary and Exploratory Efficacy Endpoint Analyses

To address the secondary objectives (sustained QFT conversion based on positive QFT test results with a follow-up of 36- and 48-months post vaccination), two analyses will be performed to assess the durability of efficacy against sustained *Mtb* infection post vaccination. The first analysis will be performed subsequent to the initial primary analysis after all participants have at least 36 months of follow-up, and the second analysis will be performed subsequent to the initial and 36-month analysis, after all participants have 48 months of follow-up. However, as noted above, depending on the timing of the sustained conversion events, the 36-month analysis may be combined with the primary analysis.

Again, stratified log-rank tests will be used to evaluate differences in the distributions of event times between the BCG vaccination and placebo groups; and hazard ratios and 95% confidence intervals will be estimated from Cox regression models, adjusted for sex and age group.

If the one-sided p-value after all participants have 36 months of follow-up is less than or equal to 0.025, durability after all participants have 48 months of follow-up will be assessed.

As such, durability after all participants have reached 36- and 48-months of follow-up will only be concluded if statistically significant differences in event times between the BCG vaccination and placebo arms were met at all prior time points evaluated. Failure to meet the primary or 36-month durability hypothesis will not result in a formal early stopping of the study.

Exploratory analyses will be performed similarly using an alternative definition of conversion as a change in IFN- γ concentration from <0.35 IU/mL to \geq 4 IU/mL.

Further similar exploratory analyses will be performed for various primary and sustained *Mtb* infection post vaccination endpoints, conversion defined by various exploratory QFT IFN- γ concentration thresholds (other than the package-insert defined 0.35 IU/mL value in the QFT assay). In addition, similar analyses will be performed using the ITT and PP efficacy populations to assess the robustness of results.

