4.2.2 Secondary Analysis

A secondary analysis will be performed to assess the durability of efficacy against (sustained) *Mtb* infection post vaccination. The analysis will be performed subsequently to the initial primary analysis after all participants included in the mITT efficacy population (Section 5.1) have least 36 months of follow-up or have prematurely discontinued the study. Agreement on specific outputs and method of distribution will be outlined in a separate document. However, depending on the timing of the sustained conversion events, the 36-month analysis may be combined with the primary analysis (and only one analysis covering all relevant endpoints will be conducted).

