7 OVERALL STATISTICAL CONSIDERATIONS

7.1 Research Hypotheses

Primary: Revaccination with BCG reduces the risk of sustained *Mtb* infection (defined for this protocol as sustained QFT conversion) versus placebo in previously BCG vaccinated, QFT negative healthy adolescents.

Secondary (hierarchical):

- Revaccination with BCG reduces the risk of sustained *Mtb* infection versus placebo in previously BCG vaccinated, QFT negative healthy adolescents, with vaccine efficacy (VE) durability that lasts at least 36 months.
- Revaccination with BCG reduces the risk of sustained *Mtb* infection versus placebo in previously BCG vaccinated, QFT negative healthy adolescents, with VE durability that lasts at least 48 months.

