7.8 Multiplicity

The primary analysis will be triggered when at least N=118 sustained *Mtb* infection events (defined as QFT conversion from a negative to positive test result, as per QuantiFERON-TB Gold Plus Package Insert) in the mITT efficacy population have accrued.

The primary efficacy endpoint (Section 4.3.1) will be analyzed using a log-rank test, stratified by sex and age group (10-11 years old, 12-14 years old, and >14 years old) to evaluate differences in the distributions of event times between the BCG vaccination and placebo groups. The two durability analyses will be performed: the first one after all participants in the mITT efficacy population have either prematurely discontinued the study or have at least 36 months of follow-up (secondary analysis; a data cutoff date will be established at the date of each participants Month 36 visit) and the second one after all participants in the mITT efficacy population have completed 48 months of follow-up at the end of study (final analysis).

Therefore, the following null hypotheses: $H_{01} \rightarrow H_{02} \rightarrow H_{03}$ will be assumed:

- H_{01} corresponding to the primary analysis (at least N=118 sustained QFT conversion events in the mITT efficacy population have accrued): $S_{s,BCG}(t) = S_{s,Pbo}(t)$
- H_{02} corresponding to the secondary analysis (when all participants have prematurely discontinued the study or have at least 36 months of follow-up): $S_{s,BCG}(t) = S_{s,Pbo}(t)$
- H₀₃ corresponding to the final analysis (when all participants have prematurely discontinued the study or have completed the study with 48 months of follow-up): S_{s,BCG}(t) = S_{s,Pbo}(t)

for strata s=1, 2, ..., 6 (6 strata = sex and age group [10-11 years old, 12-14 years old, and >14 years old]), where S(t) is the survival probability (probability that a participant's time to sustained *Mtb* infection > t).

To account for multiple testing, a step-down approach will be used to preserve the overall Type I error at a one-sided 2.5%. Specifically, if the one-sided p-value associated with the primary hypothesis H_{01} of BCG vaccine efficacy relative to placebo (p_1) is less than or equal to 0.025, the durability of the vaccine efficacy after all participants have 36 months of follow-up (H_{02}) will be formally assessed. If both H_{01} and H_{02} are rejected at one-sided 2.5% then the H_{03} will be formally assessed at one-sided 2.5%.

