9.3 Secondary Analyses

To address the secondary objectives (sustained QFT conversion based on positive QFT test results in participants with a follow-up of 36- and 48-months post vaccination), two analyses will be performed to assess the durability of efficacy against sustained *Mtb* infection post vaccination.

The first secondary analysis will be performed subsequent to or at the same time with the primary analysis after all participants have had at least 36 months of follow-up (or prematurely discontinued), and the second secondary (i.e., final) analysis will be performed subsequent to the initial and the 36-month analysis after all participants have 48 months of follow-up (or prematurely). Both analyses will be based on the mITT efficacy population.

Log-rank tests, stratified by sex and age group (10-11 years old, 12-14 years old, and > 14 years old), will be used to evaluate differences in the distributions of event times between the BCG vaccination and placebo groups. Hazard ratios and 95% confidence intervals will be estimated using stratified Cox proportional hazards regression models.

If the one-sided p-value after all participants have 36 months of follow-up is less than or equal to 0.025, durability after all participants have 48 months of follow-up will be assessed. As such, durability after all participants have reached 36- and 48-months of follow-up will only be concluded if statistically significant differences in event times between the BCG vaccination and placebo arms were met at all prior time points evaluated. Failure to meet the primary or 36- month durability hypothesis will not result in a formal early stopping of the study.

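### The 36- and 48-month durability hypotheses are decided by rerunning the primary's cumulative log-rank test on longer follow-up, so meeting them does not show protection past Month 24

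*Protocol*

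**What the plan says.** The hypotheses are about persistence. Protocol 9.1 has BCG reducing risk "with VE durability that lasts at least 36 months in all participants", and SAP 7.1 has it "with vaccine efficacy (VE) durability that lasts at least 36 months"; each then repeats the statement for 48 months. Protocol 4.1 gives the reason: "The longer follow-up will enable us to assess the duration of protection past 24 months as a secondary objective". It adds that the SAP will contain analyses of how long protection lasts.

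The decision rule is about the whole curve.

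- Protocol Table 10: "The secondary hypotheses will be met if the 1-sided p-value associated with evaluating whether the event free distribution is longer" with BCG is at or below 0.025. Apart from naming the secondary hypotheses, this is the rule for the primary.
- Protocol 9.4.1.2: "two analyses will be performed to assess the durability of efficacy against sustained" infection, again by stratified log-rank tests and Cox models.
- SAP 7.8: if the primary null is rejected, "the durability of the vaccine efficacy after all participants have 36 months of follow-up" is tested next. H01, H02 and H03 are written as the same null, equal survival functions in every stratum.
- SAP 9.3: "durability after all participants have reached 36- and 48-months of follow-up will only be concluded if statistically significant differences in event times" were found at all earlier steps.
- SAP 4.3.2 keeps the primary endpoint and cuts the first durability analysis at each participant's Month 36 visit. It sets no lower bound. SAP 9.1 starts the clock at Day 71.
- SAP 4.2.2: "the 36-month analysis may be combined with the primary analysis (and only one analysis covering all relevant endpoints will be conducted").

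**The concern.** A log-rank test from Day 71 asks whether the two curves differ over all follow-up so far. A vaccine that works for two years and then stops still leaves the curves apart at Months 36 and 48. The step-down could then declare 48-month durability under a controlled alpha although nothing was prevented after Month 24.

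This matters because the Protocol (2.2) already cites an earlier study suggesting protection for at least two years. What happens after that is a large part of what this trial adds.

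**Working it through.** **1. The plan's own figure.** With hazard ratio 0.55, one-sided alpha 0.025, 90% power and 1:1 allocation, Schoenfeld's formula gives 4 × (1.960 + 1.282)² / (ln 0.55)² = 42.03 / 0.3574 = 117.6, so 118 events. This matches Protocol 9.2.

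**2. Which late visits count.** A sustained conversion needs a positive result six months after the first one.

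- H02 is cut at Month 36, so Month 30 is its last scheduled detection visit, and the only one after Month 24.
- For H03, Protocol 4.3 does not evaluate Month 48 conversions. The late detection visits are Months 30, 36 and 42.
- SAP 7.7 lets unscheduled QFT results add to either.

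**3. Inputs.** From Protocol 9.2: 900 × 0.93 = 837 mITT per arm, 8–10% annual attack rate, 70% sustained (5.6–7.0% a year), 5% annual drop-out, one-year accrual, VE 45%. The waning profiles are assumptions; the documents give none.

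**4. Hand check for VE 45% to Month 24, then zero.** Simulated mean event counts at 8% and 10% attack rates:

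| Step | Events | After Month 24 | Late share |
|---|---|---|---|
| H02 | 158; 196 | 38; 47 | 24% |
| H03 | 228; 281 | 108; 132 | 47% |

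Taking the log hazard ratio as 0.598 for early events and 0 for late ones:

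- H02: 0.76 × 0.598 = 0.454, so cumulative VE = 1 − e^(−0.454) ≈ 36%. The expected Z is √158/2 × 0.454 = 2.85, and √196/2 × 0.454 = 3.18. Power is about 81% and 89%.
- H03: 0.53 × 0.598 = 0.317, so cumulative VE ≈ 27%. The expected Z is about 2.4 and 2.7. Power is about 66–67% and 76%.

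An unstratified simulation (1,000 trials per scenario) gave 81% and 87% for H02, and 66% and 74% for H03, in agreement.

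**5. The full sequence.** This simulation has 5,000 trials per scenario, a log-rank stratified by six sex-by-age strata, detection at six-monthly visits and H01 at the 118th confirmed event. Ranges span 8–10% attack rates.

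| True VE profile | All three steps pass |
|---|---|
| Constant 45% | 88–89% |
| 45%, zero from Month 30 | 78–84% |
| 45%, zero from Month 24 | 58–69% |
| 45%, zero from Month 18 | 31–40% |
| 45%, zero from Month 12 | 12–16% |
| Linear from 45% to zero over Months 0–36 | 26–32% |
| Linear from 45% to zero over Months 0–24 | 12–13% |

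For loss at Month 24, H02 and H03 alone passed in 57–69% in a separate run. The smaller unstratified run gave 62% and 71% for all three (Monte Carlo error about 1.5 points). With an assumed gamma frailty of variance 1 or 2, all three pass in 50–59% or 44–52%. At the maximum of 2,150 randomized (1,000 mITT per arm, two-year accrual assumed), all three pass in 63–73%.

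**6. A comparison restricted to follow-up after Month 24, on Month 48 data.** Under constant 45% VE it has 78–100 events and 74–83% power. It rejects in 2.4–2.9% of trials when late VE is zero, against a nominal 2.5%.

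**7. What else in the plan might fill the gap.** The treatment-by-log(time) term in SAP 9.1 and Appendix 7 only chooses the variance estimator. Kaplan–Meier plots are descriptive. SAP 9.4 varies QFT thresholds, and SAP 5.2 lists no time-based subgroup. Neither document has a landmark, period-specific or time-varying VE.

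**The case against.** **The sequence does respond to waning.** This stands. The tests are rerun on more data, late events without efficacy dilute them, and loss by Month 12 is mostly caught. A reader might infer that H02 and H03 pass automatically once the primary does. The table above does not support that. Only the optional combined analysis would put H01 and H02 on one dataset.

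**Waning would be visible.** This stands in part. Cumulative VE falling from about 36% to 26–27%, and the plotted curves, would let a careful reader see a decline. None of it enters the decision rule.

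**Part of this is terminology.** The endpoint is openly described by its length of follow-up, and Month 24 appears in no hypothesis, only in the rationale. That is fair, and it is why renaming is half of the remedy. The hypotheses nonetheless claim efficacy that lasts.

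**The headline profile is an illustration.** It is. An abrupt stop at Month 24 favours the early signal more than gradual loss from the start does.

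**A pooled late comparison is also limited.** This stands. If efficacy ended at Month 36, it would still reject in about 41–49% of trials. It supports some efficacy after Month 24, not durability to 36 or 48 months.

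**The late risk set is selected.** Also right. It conditions on status at Month 24, and about 30% of initial conversions are expected not to be sustained. Appendix 6 has no row of its own for a converter with both confirmation results present and one negative, so the status of reverters must be stated.

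**Conclusion.** The point holds, as a mismatch between what the secondary hypotheses claim and what their test can show. Meeting H02 or H03 establishes that the curves differ cumulatively through 36 or 48 months. It does not establish protection past Month 24. Under the plan's rates and an assumed loss of all efficacy at Month 24, the sequence passes in about 57–69% of trials, against about 88–89% under constant VE. The figure is lower with earlier or gradual waning or with marked heterogeneity of risk.

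A reader might also infer that type I error is inflated. It is not: the step-down controls it for the nulls as written. The primary hypothesis, its alpha and its 118 events are untouched. This should be fixed, but it does not threaten the trial's main result.

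**What to change.** 1. **Rename.** In Protocol 9.1, Table 10 and 9.4.1.2, and in SAP 7.1, 7.8 and 9.3, call H02 and H03 *cumulative VE through 36 (48) months of follow-up* and drop the wording that durability lasts. State that at scheduled visits H02 counts sustained conversions first detected by Month 30 and H03 by Month 42, and that unscheduled QFT results may add to these.

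2. **Add one estimate, pre-specified before the primary-analysis unblinding.** On Month 48 data, fit a Cox model stratified by sex and age group and report VE with a 95% CI. Include mITT participants who by Month 24 have had neither a sustained-conversion event nor censoring under SAP 9.1 and Appendix 6, and say explicitly how reverters are handled. Describe the result as average efficacy after Month 24 (detections at Months 30, 36 and 42), not as durability to 36 or 48 months. If a formal claim is wanted, place it after H03 in the step-down.

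3. **Keep any finer split descriptive.** Under constant 45% VE, Months 24–36 (detections at 30 and 36) would have about 53–68 events and 56–69% power. Months 36–48 (detection at 42 only) would have about 24–31 events and 30–38% power.

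**Cost.** Wording in both documents and one model on data already collected. The late comparison has about 74–83% power under constant 45% VE, so it would miss truly lasting efficacy in 17–26% of trials. Its interval is wide, roughly 14–18% to 63–65%. Conditioning on status at Month 24 can bias it. In runs with assumed gamma frailty it understated late VE (a true 45% read as 38–42%), but those runs do not cover vaccination turning sustained conversions into reversions, so the direction of bias is not settled.
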